8.3.11.3.1. Proximal Renal Tubule Dysfunctions (PRTD)

PRTD is defined as:

- Confirmed rise in serum creatinine of ≥ 0.5 mg/dL from Baseline AND serum phosphate < 2.0 mg/dL;

Either of the above accompanied by any two of the following:

- Glycosuria (≥ 250 mg/dL) in a non-diabetic;
- Low serum potassium (< 3 mEq/L);
- Low serum bicarbonate (< 19 mEq/L).

Participants meeting criteria for PRTD must return for a confirmatory assessment within 2 weeks of diagnosis. A urinalysis should also be performed at the time of the confirmatory assessment. If PRTD is confirmed participants should have study drug withheld and the investigator should contact the Study medical monitor to discuss the rationale for restarting study drugs (if appropriate). Consideration for confounding factors (e.g., NRTI backbone, other medications, dehydration, concurrent conditions) should be taken into account, and a nephrology consult may be obtained. If study drug is reinitiated, it should have been withheld for no more than 4 weeks.

8.3.11.4. Proteinuria

Participants with an abnormal urine microalbumin/creatinine ratio (> 0.3 mg/mg, > 300 mg/g, or > 34 mg/mmol) that represents a change from Baseline and no associated increase in creatinine, should have a repeat spot urine microalbumin/creatinine ratio performed within 2-4 weeks. If confirmed, then consideration should be given to additional evaluation after consultation with the study medical monitor. Additional evaluation may include a 24-hour urine protein and creatinine measurement and nephrology referral.

Participants with an abnormal urine albumin/creatinine ratio (> 0.3 mg/mg, 300 mg/g, or > 34 mg/mmol and representing a change from Baseline) and a serum creatinine increase > 45 $\mu\text{mol/L}$ (or 0.5 mg/dL) should have confirmation of both results within 2 weeks. If confirmed, the study medical monitor should be contacted immediately. Agreement on further management should be agreed between the investigator and medical monitor.

8.3.11.5. QTc Prolongation

Participants with an average QTc interval > 550 msec from three or more tracings separated by at least 5 minutes should have IP discontinued. These criteria are based on an average QTc value of triplicate ECGs. If an ECG demonstrates a prolonged QT interval, obtain 2 more ECGs over a brief period (~5-10 minutes) and use the averaged QTc values of the 3 ECGs to determine whether the participant should be discontinued from the study. If an alternative cause of the QT prolongation is determined (e.g.,

participant receiving drug known to cause prolonged QT or TdP), then IP may be restarted after consultation with, and agreement by, the Medical Monitor.

8.3.11.6. Injection Site Reactions (ISRs)

Injection site reactions will be managed through investigator assessment throughout the study. All ISRs that are either serious, Grade 3 or higher, or persisting beyond 2 weeks must be discussed with the Medical Monitor to determine etiology and assess appropriate continued study participation.

Digital photographs may be documented where possible on all participants who have an injection site reaction, with observable findings, that is either serious or Grade 3 or higher, or that persists beyond 2 weeks. Dermatology will be consulted on all participants who have an injection site reaction considered serious, Grade 3 or above, or if clinically significant and persistent beyond 30 days and others if the Investigator or Medical Monitor feels it is medically necessary.

Details regarding photo collection and any other follow up will be given by the Medical Monitor at the time of assessment.

ISR discomfort can be managed symptomatically (e.g., cold/warm compress, acetaminophen, ibuprofen) if the reaction is interfering with the participant's ability to perform activities of daily living. The required intervention should be documented on the appropriate eCRF page.

8.3.11.7. Allergic Reaction

Participants may continue study drug for Grade 1 or 2 allergic reactions at the discretion of the Investigator. The participant should be advised to contact the Investigator immediately if there is any worsening of symptoms or if further systemic signs or symptoms develop. Antihistamines, topical corticosteroids, or antipruritic agents may be prescribed.

Participants with Grade ≥ 3 allergic reactions that are considered to be possibly or probably related to the study drug should permanently discontinue the CAB LA + RPV LA regimen and the participant should be withdrawn from the study. Participants should be treated as clinically appropriate and followed until resolution of the AE.

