Injection Site Reactions (ISRs)	
Clinical, experience to date has demonstrated ISRs occur in the majority of exposed participants treated with CAB LA but are generally CCI (Grade 1) or CCI (Grade 2)
	
 • Administration advice will be given to minimize risk of poor administration technique giving rise to injection site reactions. Advice on care, monitoring, natural course, and

Potential Risk of Clinical Significance	Summary of Data/Rationale for Risk	Mitigation Strategy
	
and include events of pain, tenderness, erythema, or nodule formation of several days' duration (median duration for individual events <1 week).
 
ISRs may occur more than once in an individual participant receiving multiple injections. Although some Grade 3 ISRs were reported, overall ISRs have been well tolerated and have not to date been associated with an excess of participants withdrawing.
	
treatment of ISRs is given in study documentation
 
 • Advice will be given to participants on care of injection site on day/days immediately post administration, use of analgesia, compresses where appropriate. • Participants will be closely monitored for ISRs particularly for signs of pain, tenderness, infections, erythema, swelling, induration, or nodules (granulomas or cysts) throughout the study. • Complications of ISRs such as infections (abscess, cellulitis) and collections of fluid requiring drainage will be monitored

Hypersensitivity Reactions (HSR)
	
Hypersensitivity reactions have been reported as uncommon occurrences with integrase inhibitors, including the closely related compound dolutegravir, and were characterized by rash, constitutional findings, and sometimes, organ dysfunction, including liver injury.
 
While there have been no clinical cases of hypersensitivity to CAB to date, there is a theoretical risk of systemic or severe hypersensitivity reactions with or without hepatic
	
 • The potential risk of developing a hypersensitivity reaction post administration of IM CAB may be minimized by the use of a 4-week oral lead-in of oral CAB to determine individual safety and tolerability prior to the introduction of IM CAB if the participant is randomized to CAB LA administration and chooses to participate in the oral lead in. • Clinical assessments, laboratory tests (including

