Potential Risk of Clinical Significance	Summary of Data/Rationale for Risk	Mitigation Strategy
	
symptoms associated with use of IM CAB. The long exposures anticipated after IM CAB injection may complicate the management of a drug hypersensitivity reaction, were it to occur.
	
liver transaminases) and vital signs will be performed throughout this study (refer to Schedule of Activities, Section 1.3). Results from these assessments may aid early detection of HSR.
 
 • Oral CAB will be withdrawn immediately for participants with suspected HSR during the oral CAB lead-in phase and they would not proceed to the injection phase. Participants in the injection phase would not receive further injections. During oral and IM CAB treatment, any HSR reactions that occur would be managed supportively.

Effects in late stage pregnancy seen in non-clinical studies
	
In animal reproduction studies, CAB when administered to rats at >30 times the systemic exposure at the maximum recommended oral human dose (MRHD) of 30 mg during organogenesis through delivery, had adverse effects on labor and delivery that may be related to a delay in the onset of parturition, resulting in increased fetal mortality (stillbirths) and neonatal deaths immediately after birth.
 
A delay in the onset of parturition, increased stillbirths and neonatal deaths were observed in a rat pre- and postnatal development study at greater than 30 times the exposure at the
	
 • Pregnant females are excluded from enrolment in this study and women of childbearing potential (WOCBP) are required to adopt highly reliable means of contraception during participation and throughout the long term follow up phase of this study following exposure to CAB LA. • WOCBP are also required to undergo regular pregnancy testing throughout study conduct. Pregnant participants who remain in the study do not need pregnancy testing for the duration of the pregnancy

Potential Risk of Clinical Significance	Summary of Data/Rationale for Risk	Mitigation Strategy

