Hearing Loss ≥ 12 years of age	NA	Hearing aid or intervention not indicated	Hearing aid or intervention indicated	Profound bilateral hearing loss (> 80 dB at 2 kHz and above) OR Non-serviceable hearing (i.e., >50 dB audiogram and <50% speech discrimination)
< 12 years of age (based on a 1, 2, 3, 4, 6 and 8 kHz audiogram)	> 20 dB hearing loss at ≤ 4 kHz	> 20 dB hearing loss at > 4 kHz	> 20 dB hearing loss at ≥ 3 kHz in one ear with additional speech language related services indicated (where available) OR Hearing loss sufficient to indicate therapeutic intervention, including hearing aids	Audiologic indication for cochlear implant and additional speech-language related services indicated (where available)
Tinnitus	Symptoms causing no or minimal interference with usual social & functional activities with intervention not indicated	Symptoms causing greater than minimal interference with usual social & functional activities with intervention indicated	Symptoms causing inability to perform usual social & functional activities	NA
Uveitis	No symptoms AND Detectable on examination	Anterior uveitis with symptoms OR Medical intervention indicated	Posterior or pan-uveitis OR Operative intervention indicated	Disabling visual loss in affected eye(s)
Vertigo	Vertigo causing no or minimal interference with usual social & functional activities	Vertigo causing greater than minimal interference with usual social & functional activities	Vertigo causing inability to perform usual social & functional activities	Disabling vertigo causing inability to perform basic self-care functions
Visual Changes (assessed from baseline)	Visual changes causing no or minimal interference with usual social & functional activities	Visual changes causing greater than minimal interference with usual social & functional activities	Visual changes causing inability to perform usual social & functional activities	Disabling visual loss in affected eye(s)

Systemic

PARAMETER	GRADE 1 MILD	GRADE 2 MODERATE	GRADE 3 SEVERE	GRADE 4 POTENTIALLY LIFE- THREATENING
Acute Allergic Reaction	Localized urticaria (wheals) with no medical intervention indicated	Localized urticaria with intervention indicated OR Mild angioedema with no intervention indicated	Generalized urticaria OR Angioedema with intervention indicated OR Symptoms of mild bronchospasm	Acute anaphylaxis OR Life-threatening bronchospasm OR Laryngeal edema

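### For low-grade allergic reactions that are also suspected hypersensitivity to CAB, Section 2.3.1 stops dosing at any grade while Section 8.3.11.7 lets the Investigator continue, and the protocol does not say which governs

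*Protocol*

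**What the plan says.** **Section 2.3.1, CAB risk table, hypersensitivity row.** For the oral lead-in: "Oral CAB will be withdrawn immediately for participants with suspected HSR during the oral CAB lead-in phase", and such participants do not go on to injections. For those already on injections: "Participants in the injection phase would not receive further injections". Neither sentence sets a grade, a relatedness test or any discretion. The same row says that the long exposure after an injection may make a hypersensitivity reaction harder to manage.

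**Section 8.3.11.7, Allergic Reaction.** "Participants may continue study drug for Grade 1 or 2 allergic reactions at the discretion of the Investigator". The participant is told to contact the Investigator "if there is any worsening of symptoms or if further systemic signs or symptoms develop". The mandatory stop starts at Grade 3: "allergic reactions that are considered to be possibly or probably related to the study drug should permanently discontinue the CAB LA + RPV LA regimen".

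**Appendix 4 (Section 10.4), DAIDS table, acute allergic reaction.** Grade 1 is localized urticaria that needs no medical intervention. Grade 2 is localized urticaria that needs intervention, or "Mild angioedema with no intervention indicated".

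**The concern.** Section 2.3.1 acts on suspicion, and Section 8.3.11.7 acts on grade and relatedness. An event can meet the first trigger without meeting the second. One site could then stop dosing under Section 2.3.1 while another gives the next injection under Section 8.3.11.7, each following the protocol.

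Two things are at stake. The first is participant safety: the next dose is a long-acting injection, and Section 2.3.1 reports residual CAB for more than a year in some people after stopping. The oral lead-in, which Section 2.3.1 offers as a way to reduce the HSR risk, is optional, so direct-to-injection participants rely more on the stopping rule. The second, and smaller, is consistency of a stated safety endpoint, discontinuation of treatment due to adverse events, which would depend partly on which section a site applied.

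**Working it through.** The protocol gives no figure to reproduce here. The check sets the rules side by side and asks where they overlap.

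**Step 1: what each section covers.** Section 2.3.1 describes integrase-inhibitor class reactions that "were characterized by rash, constitutional findings, and sometimes, organ dysfunction, including liver injury". For CAB it says "there is a theoretical risk of systemic or severe hypersensitivity reactions with or without hepatic" symptoms. The CAB risk is worded as systemic or severe, so a systemic reaction need not be severe to qualify. Section 8.3.11.7 covers allergic reactions to study drug and sorts them by grade. Its reference to further systemic signs implies that a reaction allowed to continue may already have some.

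**Step 2: what other stops exist.**
- Section 7.1, mandatory list: Grade 2 rash with systemic involvement, or rash of Grade 3 or higher, when no compelling alternative cause is found. The list has no entry for allergic reaction or suspected HSR.
- Section 7.1.2, Table 3: ALT at least 3×ULN (or at least 3×baseline if baseline ALT exceeds 1.5×ULN) with symptoms attributed to liver injury or hypersensitivity.
- Section 8.3.11.9: rash of Grade 2 or higher with an ALT increase.
- Section 8.3.10.2 gives general discretion for Grade 1 or 2 events and makes no exception for HSR.

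**Step 3: apply the rules to presentations.**

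| Presentation | 2.3.1 | 8.3.11.7 | Other stop | Result |
|---|---|---|---|---|
| Isolated localized Grade 1 urticaria | Need not apply | May continue | None | No conflict required |
| Grade 2 mild angioedema, suspected HSR, no rash, no ALT rise | Stop | May continue | None | Conflict |
| Low-grade reaction with systemic signs, suspected HSR, no ALT rise, not a Grade 2 rash | Stop | May continue | None | Conflict |
| Grade 2 rash with systemic involvement, no compelling alternative cause | Stop if suspected HSR | May continue if classed as allergic | 7.1 | Settled by 7.1 |
| Hypersensitivity symptoms with ALT at the Table 3 threshold | Stop if suspected HSR | May continue if Grade 1 or 2 | 7.1.2 | Settled by 7.1.2 |
| Grade 2 rash with ALT increase | Stop if suspected HSR | May continue if classed as allergic | 8.3.11.9 | Settled by 8.3.11.9 |
| Grade 3 or higher, suspected HSR and judged related | Stop | Stop | – | Agree |

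**Step 4: does anything rank the sections?** No. Section 2.3 introduces the table as the risk assessment and mitigation strategy for this protocol, so it is not offered as background only. Its liver row points to Section 7.1.2.1 and its RPV rash row to Section 8.3.11.9. The CAB hypersensitivity row points only to the Schedule of Activities and never to Section 8.3.11.7.

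**Step 5: number exposed to the ambiguity.** With 654 participants randomized 2:1, 654 × 2/3 = 436 are assigned to CAB + RPV. The other 654 × 1/3 = 218 are assigned to BIK and are an upper bound on those who could switch in the Extension Phase. These are participants at risk, not expected events.

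**The case against.** A reader might infer that every Grade 1 or 2 allergic reaction falls under opposite rules. The documents do not support that. The two sections use different terms, Section 2.3.1 describes HSR as systemic or severe, and a localized wheal need not be that syndrome. Section 2.3.1 also lets Grade 1 or 2 rash continue on clinical judgment in its RPV row, so it does not treat every low-grade skin event as HSR. Its HSR row is specific to CAB, and the word suspected appears only in the oral lead-in sentence; the injection sentence carries it by context. Several low-grade presentations that resemble the described syndrome already have explicit stops. All of this stands and narrows the point.

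It can also be said that Section 8.3.11.7 only permits continuation, so an Investigator who suspects HSR can stop under Section 2.3.1 and breach neither section. That is true for that Investigator. It does not remove the conflict, because Section 8.3.11.7 grants a discretion that Section 2.3.1 does not allow. An Investigator who suspects HSR and continues has followed one section and departed from the other.

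A reader might also infer a material effect on the safety results. With no CAB hypersensitivity cases reported and no event rate in the protocol, that cannot be claimed. Prolonged exposure follows any injection already given; only the exposure from a further injection depends on this wording.

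**Conclusion.** The inconsistency holds within a limited overlap: Grade 1 or 2 allergic reactions that are also suspected HSR to CAB and are not caught by the rash or ALT stops. Grade 2 mild angioedema without rash or ALT rise is the clearest case. The conclusion assumes that an Investigator could reasonably suspect HSR in such a reaction, and that the injection-phase sentence of Section 2.3.1 applies to suspected HSR, as its context indicates. No count of events can be given. Few are expected, and any effect on the discontinuation endpoint is likely to be small. The passages should still be reconciled, because the consequence of an individual event is long-lasting and the correction is cheap. Nothing here bears on the primary analysis, and no view is taken on which clinical rule is right.

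**What to change.** Reconcile the hypersensitivity row of Section 2.3.1 with Section 8.3.11.7 into one rule, stated once. The text should:
- say how suspected HSR to study drug is distinguished from a Grade 1 or 2 allergic reaction;
- say whether grade or relatedness bears on the stop for suspected HSR, and whether the rule covers CAB only or the whole regimen;
- be cross-referenced from the mandatory discontinuation list in Section 7.1, together with Table 3 in Section 7.1.2 and the rash rules in Section 8.3.11.9.

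The sponsor's medical team decides which rule stands. The cost is protocol wording only, with no new visits, tests or staff.

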8.3.11.8. Abacavir Hypersensitivity Reaction (ABC HSR)

If a study participant discontinues study IP, enters into the LTFU period and are administered an ABC-containing product, please follow the information contained within this section.

Background

The most significant toxicity associated with ABC is the well-characterized drug-related hypersensitivity reaction (HSR). A detailed clinical description of this reaction (including the type and severity of events that can occur on re-challenge or reintroduction following ABC interruption for non-HSR reasons) and guidance regarding its

management are included in the Local Country Prescribing Information for EPZICOM. Investigators must familiarize themselves with this information on ABC HSR in the Local Country Prescribing Information for each of these products prior to initiating participants on ABC therapy.

Studies have shown that carriage of the *HLA-B*5701* allele is associated with a significantly increased risk of a HSR to ABC. In the prospective study CNA106030 (PREDICT-1), the use of pre-therapy screening for the presence of *HLA-B*5701* and subsequently avoiding ABC in *HLA-B*5701* positive patients, significantly reduced the incidence of clinically suspected ABC HSR from 7.8% (66 of 847) to 3.4% (27 of 803) ($p < 0.0001$). In clinical studies EPZ108859 (ARIES) and CNA109586 (ASSERT), 0.8% (4/515) and 3.1% (6/192) of participants who were *HLA-B*5701* negative and who received ABC developed a clinically suspected ABC HSR, respectively.

In any participant treated with ABC, the clinical diagnosis of suspected HSR (as detailed in the Local Country Prescribing Information) must remain the basis of clinical decision making. Regardless of *HLA-B*5701* status, it is important to permanently discontinue ABC and not re-challenge with ABC (i.e., ZIAGEN, EPZICOM/KIVEXA, TRIZIVIR, or TRIUMEQ) if a HSR cannot be ruled out on clinical grounds, due to the potential for a severe or even fatal reaction.

8.3.11.8.1. Essential Patient Information

With reference to Local Country Prescribing Information and the ‘Participant Information and Consent Form’, Investigators must ensure that participants are fully informed regarding the following information on the hypersensitivity reaction prior to commencing ABC therapy:

- Participants must be made aware of the possibility of a hypersensitivity reaction to abacavir that may result in a life-threatening reaction or death and that the risk of a hypersensitivity reaction is increased in individuals who are *HLA-B*5701* positive.
- Participants must also be informed that *HLA-B*5701* negative individuals can also experience abacavir hypersensitivity reaction. Therefore, ANY participant who develops signs or symptoms consistent with a possible hypersensitivity reaction to abacavir MUST CONTACT their doctor IMMEDIATELY.
- Participants who are hypersensitive to abacavir should be reminded that they must never take any abacavir containing medicinal products (e.g., ZIAGEN, EPZICOM, KIVEXA, TRIZIVIR, or TRIUMEQ) again, regardless of their *HLA-B*5701* status.
- In order to avoid restarting abacavir, participants who have experienced a hypersensitivity reaction should be asked to return any remaining EPZICOM / KIVEXA tablets to the Investigator or site staff.
- Participants, who have stopped abacavir for any reason, and particularly due to possible adverse reactions or illness, must be advised to contact their doctor

before restarting EPZICOM / KIVEXA as more severe symptoms may recur within hours and may include life-threatening hypotension and death.

- Each participant should be reminded to read the Package Leaflet included in the EPZICOM / KIVEXA pack. They should be reminded of the importance of removing the Alert Card included in the pack and keeping it with them at all times.

8.3.11.8.2. Reporting of Hypersensitivity Reactions

If a clinically suspected case of HSR to ABC meets one of the International Conference on Harmonization (ICH E2A), 1994 definitions of seriousness listed in Section 10.2.2 then, in addition to reporting the case as an SAE, the ABC HSR eCRF should also be completed within one week of the onset of the hypersensitivity reaction. Clinically suspected cases of HSR to ABC that do not meet criteria as an SAE can be recorded as an AE.

